Pleth variability index (PVI) as a measure of volume status during transcatheter mitral valve repair

Official Title: Pleth variability index (PVI) as a measure of volume status during transcatheter mitral valve repair

NCT Number: NCT03993938

Document Date: 5/30/2022

Study Protocol

The study aims (1) To measure the intraprocedural change in pleth variability index (PVI) during transcatheter mitral valve repair (TMVR) and 2. To compare PVI with left atrial pressure (LAP) prior to and after mitral clip deployment

The purpose of the study is to determine if pleth variability index (PVI) can be used during transcatheter mitral valve repair as a monitor of volume status and understand its importance as a noninvasive hemodynamic monitor by comparing it to invasive indices including left atrial pressure.

Transcatheter mitral valve repair in the form of MitraClip® is a safe and effective alternative to surgical mitral valve repair/replacement in patients with high operative morbidity and mortality risk. Successful MitraClip application depends on intraprocedural quantification of mitral regurgitation and left atrial pressure (LAP) monitoring. Large volumes of intravenous fluids administered during TMVR may result in significant changes in LAP and hemodynamics. Studies indicate that LAP measured immediately after transseptal puncture would be significantly different than LAP measured immediately prior to MitraClip leaflet grasping. The pleth variability index (PVI) is a noninvasive, dynamic index based on analysis of the respiratory variations in the plethysmographic waveform recorded transcutaneously by the pulse oximeter. Studies demonstrate that PVI is accurate in predicting fluid responsiveness in mechanically ventilated adult patients. In this study, we wish to measure PVI during TMVR and correlate with invasive indices such as left atrial pressure (LAP) and stroke volume variation. Our study hopes to provide a real-time non-invasive alternative to invasive indices to better guide fluid management and improve hemodynamics.

Transcatheter mitral valve replacement is becoming increasingly popular in the management of mitral regurgitation in patients with high operative morbidity and mortality. Accurate fluid management is key in hemodynamics in these patients. Current practice is to rely on invasive indices such as left atrial pressure which cannot practically be measured in real-time. Based on the principles of PVI, using this noninvasive modality can potentially change current practice during TMVR and improve patient outcomes with minimal risk.

Inclusion Criteria: Male and female patients with mitral regurgitation undergoing transcatheter mitral valve repair (TMVR) with Mitra-Clip at Henry Ford Hospital - Main Campus.

Exclusion Criteria: MitraClip procedure unsuccessful (defined as no clip deployment and/or procedural interruption due to complication), or patients in whom PVI monitoring was not performed due to technical issues.

Statistical Analysis Plan

Study design – Prospective cohort

Sample size – 30

The sample size was calculated based the on the correlation of delta PVI and delta LAP: the null hypothesis correlation of 0 and the alternative hypothesis correlation of 0.6 using a two-sided hypothesis test with a significance level of 0.05. The power was set at 0.8 and 0.95 to determine a possibly sufficient range for sample size. The results indicated that a minimum of 19 and a maximum of 30 were warranted. Thus, we plan to include a total of 30 patients for this study.

Masimo Radical-7® probe to be attached to patient's finger along with standard ASA monitors at the start of procedure. Intraprocedure LAP (v-wave and mean) to be recorded prior to and after MitraClip deployment. Data to be analyzed - age, sex, BMI; Preprocedure EF, PAP, rhythm, MR severity; HR, SBP, DBP, MAP every 5 minutes; SPV, PPV, PVI every 5 minutes; LAP prior to mitraclip deployment; LAP after mitraclip deployment

Patients baseline characteristic and clinical data will be summarized with mean, SD or median and interquartile range (IQR) for continuous variables, and frequency and proportion for categorical variables. The change for PVI, and LAP between pre and post will be calculated as delta PVI, delta and delta LAP, respectively. Spearman correlation coefficient will be used to study the correlation between delta PVI and delta LAP. A p-value<0.05 will be considered statistically significant.

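### The sample sizes of 19 and 30 fit a Pearson test, but the planned test is Spearman, whose power at n=30 under normality is about 0.92 or 0.94, not 0.95

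*Combined protocol and SAP*

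**What the plan says.** The Sample size paragraph of the SAP defines the target in general terms: "The sample size was calculated based the on the correlation of delta PVI and delta LAP". The hypotheses are "the null hypothesis correlation of 0 and the alternative hypothesis correlation of 0.6", "using a two-sided hypothesis test with a significance level of 0.05". Two power levels are used: "The power was set at 0.8 and 0.95 to determine a possibly sufficient range for sample size". The outcome is "The results indicated that a minimum of 19 and a maximum of 30 were warranted", followed by "Thus, we plan to include a total of 30 patients for this study". The paragraph does not name a correlation coefficient, a distribution or a calculation method.

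The closing analysis paragraph of the SAP names the test: "Spearman correlation coefficient will be used to study the correlation between delta PVI and delta LAP", with the criterion "A p-value<0.05 will be considered statistically significant". It is the only test of this association in the plan. Nothing in the Study Protocol section adds to it.

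**The concern.** A sample-size calculation should describe the test that will be run. Pearson and Spearman are different tests. With bivariate-normal data the rank test is somewhat less powerful, and the same dependence has a smaller Spearman value than Pearson value. If the sizes come from a Pearson calculation, the power attached to them does not carry over unchanged to the planned analysis.

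This calculation is the only justification given for 30 patients. Because the coefficient is not named, a reader cannot be sure which correlation the study is powered to detect, nor recover 19 and 30 with the named test under normality. What is at stake is the accuracy of the power statement. The adequacy of n=30 is not in question.

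**Working it through.** **Inputs from the SAP.** Correlation 0 versus 0.6; two-sided alpha 0.05; power 0.80 and 0.95; resulting sizes 19 and 30; planned size 30; planned test Spearman. Pairing 19 with 0.80 and 30 with 0.95 is the natural reading of the paragraph. Bivariate normality is my assumption, because the plan states no distribution.

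**Step 1: reproduce the plan's sizes with a Pearson test.** The Fisher-z formula is n = 3 + [(z₀.₉₇₅ + z_power) / atanh(0.6)]², with atanh(0.6) = ½·ln(1.6/0.4) = 0.6931.

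- Power 0.80: 3 + [(1.960 + 0.842)/0.6931]² = 19.3
- Power 0.95: 3 + [(1.960 + 1.645)/0.6931]² = 30.05

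These round to 19 and 30. With the usual bias term r/(2(n−1)), the smallest sizes are exactly 19 (power 0.810) and 30 (power 0.955). A one-sided version gives 15.9 and 25.5 and does not match.

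Simulation of the Pearson t-test (500,000 replicates) agrees:

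| n | Pearson power, correlation 0.6 |
|---|---|
| 18 | 0.789 |
| 19 | 0.814 |
| 29 | 0.949 |
| 30 | 0.955 |

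So 19 and 30 are the smallest sizes reaching 0.80 and 0.95 for a Pearson test. That the plan used Pearson is an inference from this match.

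**Step 2: translate 0.6 between the coefficients.** Under bivariate normality, Spearman = (6/π)·asin(Pearson/2).

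- If 0.6 is the Pearson value, Spearman = (6/π)·asin(0.3) = 0.582.
- If 0.6 is the Spearman value, Pearson = 2·sin(π·0.6/6) = 0.618.

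**Step 3: power of the planned Spearman test.** Simulation with 1,000,000 replicates, two-sided 0.05, t-approximation critical value:

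| n | Power setting in plan | Spearman power, 0.6 = Pearson | Spearman power, 0.6 = Spearman |
|---|---|---|---|
| 19 | 0.80 | 0.745 | 0.777 |
| 30 | 0.95 | 0.925 | 0.943 |

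Shortfall at n=30: 0.950 − 0.925 = 0.025, or 0.950 − 0.943 = 0.007.

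**Step 4: check by formula.** Taking the variance of the Fisher-transformed Spearman coefficient as 1.06/(n−3), power is Φ(atanh(ρ)·√[(n−3)/1.06] − 1.960). At n=30, √(27/1.06) = 5.047.

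- ρ = 0.582: Φ(0.6654 × 5.047 − 1.960) = Φ(1.398) = 0.919
- ρ = 0.6: Φ(0.6931 × 5.047 − 1.960) = Φ(1.538) = 0.938

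Both are slightly below the simulated values and lead to the same conclusion.

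**Step 5: check the critical value.** The simulated null rejection rate is 0.0516 at n=19 and 0.0506 at n=30. With critical values calibrated to the simulated null (0.4579 and 0.3615), power is 0.740 or 0.772 at n=19 and 0.924 or 0.942 at n=30. The result does not depend on the approximation.

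**Step 6: vary the distribution.** Spearman power at n=30 in assumed scenarios:

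| Distribution of the changes | Pearson = 0.6 | Spearman = 0.6 |
|---|---|---|
| Bivariate normal | 0.925 | 0.943 |
| Lognormal, log-SD 0.5 | 0.952 | 0.943 (ranks unchanged) |
| Lognormal, log-SD 1 | 0.990 | 0.943 (ranks unchanged) |
| t, 5 df | 0.900 | 0.932 |
| t, 3 df | 0.880 | 0.925 |

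**The case against.** The strongest reply is that nothing of substance changes. The plan calls its two power levels a way to find a plausible range and takes the upper end. Spearman power at n=30 lies between 0.80 and 0.95 under normality on either reading of 0.6. Since Spearman is the only coefficient the plan names, 0.6 may well mean the Spearman value, and then the gap is 0.7 points. The 0.6 itself has no stated source. Pearson power at n=30 falls from 0.955 to 0.947 if the correlation is 0.59 and to 0.928 if it is 0.57, while a Spearman value of 0.61 gives the Spearman test 0.952. The gap is therefore no larger than the effect of a small change in the assumption. Under skewed distributions it can disappear altogether.

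Most of this stands, and it is why the point is minor and why n=30 should not change. Two things remain. Under the normality assumption that reproduces the plan's own sizes, neither reading of 0.6 gives the planned test 0.95 power. And the text never says that 0.6 is the Spearman value, so the more favourable reading has to be supplied by the reader. It is also fair that 19 is not the planned size, so the larger shortfall there has no practical consequence.

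**Conclusion.** The concern holds as a minor error in the power statement. The plan's arithmetic is correct for a Pearson test, but the pairing of 30 patients with 0.95 power is not confirmed for the Spearman test. Under bivariate normality it is too high by about 2.5 points (0.6 as Pearson) or 0.7 points (0.6 as Spearman). The conclusion rests on that distributional assumption and on the inference that a Pearson calculation was used. Across the distributions in Step 6, power at n=30 runs from 0.880 to 0.990, always above 0.80, so the sample size is adequate as it stands.

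**What to change.** Keep n=30. State which coefficient 0.6 refers to, and replace the 19-to-30 statement with one sentence. If Pearson is meant: *Assuming bivariate-normal changes, 30 analysed patients give the two-sided 0.05 Spearman test about 92% power if the Pearson correlation of delta PVI and delta LAP is 0.6.* If Spearman is meant, end the sentence instead with *about 94% power if the Spearman correlation is 0.6.* The normality assumption serves only the power statement and does not restrict the rank-based analysis. The word *analysed* matters because the figure applies to patients who contribute both changes.

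The cost is one SAP sentence and a stated power that is lower by about 2.5 or 0.7 points. No replacement range and no extra patients are needed.

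### Does leaving heart rhythm out of the single delta PVI–delta LAP correlation make a null result uninterpretable?

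*Combined protocol and SAP*

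**What the plan says.** The Study Protocol background describes PVI as a "dynamic index based on analysis of the respiratory variations in the plethysmographic waveform recorded transcutaneously by the pulse oximeter" and reports from earlier studies that "PVI is accurate in predicting fluid responsiveness in mechanically ventilated adult patients". It does not mention rhythm.

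The Inclusion Criteria admit "Male and female patients with mitral regurgitation undergoing transcatheter mitral valve repair (TMVR) with Mitra-Clip" at one hospital. The Exclusion Criteria remove unsuccessful procedures and "patients in whom PVI monitoring was not performed due to technical issues". Neither refers to rhythm.

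The Statistical Analysis Plan collects "Preprocedure EF, PAP, rhythm, MR severity". Variables of this kind are summarized by "frequency and proportion for categorical variables". The only inferential analysis is stated in one sentence: "Spearman correlation coefficient will be used to study the correlation between delta PVI and delta LAP". No stratum, covariate or sensitivity analysis uses rhythm. The sample size of 30 rests on a correlation of 0.6 against 0, two-sided 0.05, with 19 patients for power 0.8 and 30 for power 0.95.

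**The concern.** An index of respiratory variation is informative only so far as the variation it picks up is respiratory. If the beat is irregular, some of the variation may come from the heart, and delta PVI may then be noisier in those patients. The plan enrols patients whatever their rhythm, records the rhythm, and then only describes it.

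If the relation between delta PVI and delta LAP were weaker in irregular rhythm, a non-significant overall correlation would have two possible explanations: PVI does not follow LAP at all, or it follows LAP in regular rhythm and the overall estimate is diluted. The plan has no pre-specified estimate to tell these apart, and a split chosen after seeing the data would carry little weight. Since rhythm is already collected, a supportive estimate by rhythm looks like a cheap remedy.

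**Working it through.** **1. The plan's own figure.** Inputs from the Statistical Analysis Plan: correlation 0.6 against 0, two-sided 0.05, power 0.8 and 0.95. By Fisher's z, n = ((z for alpha + z for power) / atanh(0.6))² + 3, with atanh(0.6) = 0.693.

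- Power 0.8: ((1.960 + 0.842) / 0.693)² + 3 = 19.3
- Power 0.95: ((1.960 + 1.645) / 0.693)² + 3 = 30.05

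These match the stated 19 and 30 apart from rounding. Simulated Spearman power at n=30 and a true correlation of 0.6 is 0.92 to 0.93. The sample size is not in error.

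**2. How much dilution could there be?** Everything about irregular rhythm here is an assumption. Take n=30, a correlation of 0.6 in regular rhythm, and 20% or 40% irregular (6 or 12 patients). Two models were simulated. In the first, irregular-rhythm patients have a lower correlation at unchanged variance. In the second, they have independent noise added to delta PVI, which is closer to the mechanism proposed.

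| Assumption for irregular rhythm | Pooled power, 20% / 40% irregular | Pooled non-significant but regular rhythm significant, 20% / 40% |
|---|---|---|
| Correlation 0 | 0.74 / 0.47 | 14% / 29% |
| Correlation 0.3 | 0.85 / 0.74 | 5% / 10% |
| Added noise, SD equal to that of delta PVI | 0.87 / 0.81 | 4% / 7% |
| Added noise, twice that SD | 0.78 / 0.61 | 11% / 20% |

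Regular rhythm alone gives power 0.85 (n=24) or 0.72 (n=18). It therefore does worse than the pooled test under the smaller noise and better under the larger. The lowest figure, 0.47, needs 40% irregular and a correlation of exactly 0, which means no signal at all rather than a noisy one. Also, a rhythm-related offset that is the same before and after clip deployment cancels in delta PVI. Only beat-to-beat noise that survives in the index, or a change of rhythm between the readings, would matter.

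**3. Could a split by rhythm separate the two explanations?** Use Fisher's z with standard error √(1.06/(n−3)), and 95% limits tanh(atanh(r) ± 1.96 × SE).

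- n=18, r=0.6: SE = √(1.06/15) = 0.266; interval 0.17 to 0.84
- n=12, r=0: SE = √(1.06/9) = 0.343; interval −0.59 to 0.59
- n=6, r=0: SE = √(1.06/3) = 0.594; interval −0.82 to 0.82

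The interval for regular rhythm overlaps both of the others. For a difference between 18 and 12 patients, SE = √(1.06/15 + 1.06/9) = 0.434.

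- 0.6 against 0: 0.693/0.434 = 1.60, and 1.60 − 1.96 = −0.36, so power is about 0.36 (0.33 simulated)
- 0.6 against 0.3: (0.693 − 0.310)/0.434 = 0.88, so power is about 0.14 (0.13 simulated)

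**4. What would the split show if rhythm had no effect?** Put 0.6 in both groups. With 18 and 12 patients the separate tests have power 0.72 and 0.50, so significance in regular rhythm only occurs with probability 0.72 × (1 − 0.50) = 0.36. With 24 and 6 patients simulation gives about two thirds. The split would often suggest a rhythm effect that does not exist.

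**The case for a change.** The best case for the concern is that the inference from the definition of PVI is reasonable, every factual statement about the plan is correct, and both models lower the power. The addition would be cheap: one variable already collected, estimates with confidence intervals, a supportive label, and no change to the main test, eligibility or enrolment. If many patients had an irregular rhythm and the added noise were large, a null result would be hard to explain.

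It stands that the plan has no pre-specified way to explain a null result by rhythm, and that a team wishing to explore this would do better to say so in advance. The step from there to a defect does not stand. A null result would still mean that the hypothesized association was not shown in the patients enrolled, which is a readable answer to the question asked. Dilution does not undermine a significant result. The split could not count as a positive result, and by its own intervals it could seldom separate the two explanations. Nor is it purely a matter of wording: regular and irregular are not defined in the plan, and the one listed rhythm item is taken before the procedure, while the supposed noise arises when PVI is read. Ejection fraction, pulmonary artery pressure and MR severity stand in the same list with the same descriptive role, and the documents give no reason to single out rhythm.

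**Conclusion.** The concern does not hold. The plan asks whether PVI follows LAP in patients undergoing this repair, enrols them without regard to rhythm, and tests that with one correlation whose sample size reproduces. No number, rule or analysis is shown to be wrong.

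The possible loss of power runs from slight (0.87) to severe (0.47) over the values tried. The documents supply neither the share of irregular rhythm nor its effect on PVI, so no point in that range can be claimed for this trial. The split by rhythm would leave every conclusion of the trial unchanged, with about one chance in three of showing even a difference of 0.6 against 0. Whether to add such an exploratory estimate in a 30-patient, single-centre cohort is a matter on which reasonable statisticians differ. The power and discordance figures assume bivariate normal data (plus normal noise in the noise model) and a true correlation of 0.6 in regular rhythm. The judgement that the main analysis is sound does not depend on them.

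### Does the absence of confidence intervals for the PVI change and for Spearman's rho call for a change to the plan?

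*Combined protocol and SAP*

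**What the plan says.** The Study Protocol section gives two aims. The first is "To measure the intraprocedural change in pleth variability index (PVI) during transcatheter mitral valve repair (TMVR"); the second is "To compare PVI with left atrial pressure (LAP) prior to and after mitral clip deployment".

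The Statistical Analysis Plan handles both briefly:

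- **Data.** The list of data to be analysed includes "SPV, PPV, PVI every 5 minutes", with LAP taken once before and once after clip deployment.
- **Summaries.** "Patients baseline characteristic and clinical data will be summarized with mean, SD or median and interquartile range (IQR) for continuous variables".
- **Change scores.** "The change for PVI, and LAP between pre and post will be calculated as delta PVI, delta and delta LAP, respectively".
- **Association.** "Spearman correlation coefficient will be used to study the correlation between delta PVI and delta LAP".
- **Decision rule.** "A p-value<0.05 will be considered statistically significant".
- **Sample size.** It rests on the correlation alone: "the null hypothesis correlation of 0 and the alternative hypothesis correlation of 0.6", two-sided 5% level, with 19 patients for 80% power and 30 for 95%.

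Neither section mentions a confidence interval, a standard error, or a paired or repeated-measures analysis of PVI.

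**The concern.** A measurement aim ends in an estimate, and an estimate from 30 patients means little without its precision. Read literally, the plan computes the PVI change for each patient and then uses it only as an input to a correlation. SD and IQR, if reported, describe how patients differ from one another, not how well the average change is known.

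The correlation raises a similar worry. The single inferential statement is a test against zero. The stated purpose is to learn whether PVI could stand in for invasive measures, and rejecting zero does not settle that. A barely significant result could be read as support when the data are compatible with almost no relation.

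At stake is a report that claims a PVI change, or a useful PVI–LAP relation, without showing how uncertain either one is.

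**Working it through.** **Inputs.** From the Statistical Analysis Plan: n = 30, null correlation 0, alternative 0.6, two-sided alpha 0.05, power 0.80 and 0.95. The documents give no SD for PVI, so widths are in SD units.

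**1. The plan's own sample size.** The plain Fisher z formula is n = ((z for alpha/2 + z for power) / atanh(0.6))² + 3, with atanh(0.6) = 0.6931.

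- 80% power: ((1.960 + 0.842)/0.6931)² + 3 = 19.3.
- 95% power: ((1.960 + 1.645)/0.6931)² + 3 = 30.05.

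Adding the usual bias term r/(2(n − 1)) to atanh(r), power is 0.786 at 18 and 0.810 at 19; it is 0.948 at 29 and 0.955 at 30. The smallest sizes that meet the targets are therefore 19 and 30, exactly as stated.

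**2. Interval for the PVI change.** For the mean paired change, the 95% half-width is t(0.975, 29)/√30 × SD of the change = 2.045/5.477 = 0.373 SD. This uses only the SD of the change and n, so a report of mean and SD fixes the interval.

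If a report gave pre and post PVI separately and omitted the change, the within-patient correlation c would be needed. With equal SDs, SD of the change = SD × √(2(1 − c)):

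| c (assumed) | SD of change / SD of PVI | 95% half-width, in SD of PVI |
|---|---|---|
| 0 | 1.414 | 0.528 |
| 0.5 | 1.000 | 0.373 |
| 0.9 | 0.447 | 0.167 |

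That threefold spread arises only if the report leaves out a quantity that the plan explicitly defines for each patient.

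**3. Interval for rho.** The significance threshold at n = 30 is t/√(t² + 28) with t(0.975, 28) = 2.048, giving |rho| = 0.361. The Bonett–Wright interval is tanh(atanh(r) ± 1.96 × √((1 + r²/2)/(n − 3))).

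- r = 0.40: SE = √(1.08/27) = 0.200; 0.4236 ± 0.392; back-transformed, 0.032 to 0.673 (p = 0.029).
- r = 0.60: SE = √(1.18/27) = 0.209; 0.6931 ± 0.410; back-transformed, 0.276 to 0.802.

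Only r and n enter, so a reader can compute this from the planned output.

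**4. What stating the intervals would alter.** The planned p-value rule would still decide. The lower Bonett–Wright limit reaches zero at r = 0.371 (p = 0.043), so test and interval disagree for |rho| between 0.361 and 0.371. In simulation under bivariate normality (200,000 replicates) this happened in 0.7%, 1.6%, 2.5% and 0.8% of trials at true rho 0, 0.2, 0.4 and 0.6. The interval can therefore add a small borderline inconsistency, but it cannot change the decision.

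**The case for a change.** The best case for a change is that the gap falls on the first-listed aim, and that the descriptive sentence does not fully close it. It allows median and IQR instead of mean and SD, and then the interval for the change can only be approximated. It also does not say outright that the change itself will be summarised. For the correlation, a significant 0.40 with limits of 0.03 and 0.67 shows how little the test alone conveys, and the documents have hopes of altering practice. Two sentences would cover both.

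Much of this stands as good reporting advice, but as grounds for revising the plan it is weak, for four reasons.

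- PVI is named among the data to be analysed and is clinical data on any ordinary reading. Since the change is also defined patient by patient, the natural reading is that it will be summarised.
- The first aim carries no hypothesis, threshold or power. A descriptive result is a defensible minimum for a cohort of this size.
- The coefficient is the planned analysis, so its magnitude will be reported. A report giving only a p-value is not what the plan describes.
- The addition is not as simple as it looks. A Hodges–Lehmann interval, the usual companion to rank methods, targets the pseudomedian, which equals the median change only under symmetry. With strongly skewed (exponential) differences at n = 30, its nominal 95% limits covered the median in about 86% of simulated samples. More basically, PVI is recorded every five minutes and the plan does not say which readings count as pre and post. Any interval depends on that choice, so specifying an interval alone would not pin down the quantity.

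**Conclusion.** No change follows. The observation is accurate: no interval is planned for the PVI change or for rho. It is a gap that analysts fill routinely when they report, using data and output the plan already provides. Followed as written, the plan still gives a legitimate summary of the PVI change and a valid Spearman test; no bias or wrong conclusion has been shown.

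The information at issue is a half-width of 0.37 SD for the mean change and, for rho, limits of roughly 0.03 to 0.67 at 0.40 or 0.28 to 0.80 at 0.60. Readers can obtain both if mean, SD, rho and n are reported. The residual loss is confined to a report that gives only median and IQR, or only separate pre and post summaries.

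This conclusion assumes that the descriptive sentence covers the PVI change and that rho is reported with the number of patients analysed. The widths assume that all 30 contribute, and the t-interval assumes that the mean of 30 changes is close to normal.
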